The Efficacy and Safety of Silodosin Singly or Combined with Ningmitai Capsules in the Treatment of Benign Prostatic Hyperplasia (BPH) Complicated with Lower Urinary Tract Symptoms (LUTS) —A Multicenter, Prospective, Randomized, Double-blind, Positive Controlled Study

Date: September 8, 2022

Statistical analysis Plan

1.Statistical analysis of population:

- (1) **FAS:** According to the basic principle of intentionality analysis (ITT), all the randomized subjects with more than one medication record and effectiveness evaluation were included in the full analysis set. The total analysis set is the main validity evaluation population of this study.
- (2) **PPS:** Include all subjects who have completed the treatment stipulated in the scheme or have not seriously violated the trial scheme. The exact definition of the serious violation scheme will be finalized during the data review. PPS is the secondary analysis population of validity, but if its results are inconsistent with the full analysis set, it is necessary to analyze the inconsistent results in detail.
- (3) **SS:** Defined as all subjects who were randomized and received at least one trial drug treatment. The safety analysis set is the safety evaluation population of this study.

2.Statistical analysis method:

- (1) **General principle:** All statistical analysis shall be processed by SPSS 23.0 and above statistical software, and shall be carried out according to the pre-established statistical analysis plan. Measurement data are described by mean, standard deviation, median, quartile, maximum and minimum. The counting data are described by frequency and percentage. After 12 weeks of treatment, the changes of IPSS scores between Tamsulosin + placebo group and Silodosin + placebo group were compared by non-inferior test, while the changes of IPSS scores between Ningmitai + Silodosin group and Silodosin + placebo group were compared by superior test, and the test levels were $\alpha = 0.025$ (unilateral). Other hypotheses were tested by two-side test with a test level of $\alpha=0.05$, and the secondary index was adjusted by Bonferroni method with a test level of $\alpha=0.0167$.

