- (2) **Balance analysis of baseline value:** Comparability analysis of demographic characteristics, general situation and baseline situation (before treatment) of the two groups of data. Among them, t test or Wilcoxon rank sum test was used for measurement data and grade data, and χ^2 test or Fisher exact probability method was used for classification data.
- (3) **Effectiveness analysis:** Conducted in FAS and PPS at the same time.

① **Main endpoint indicators:** After 12 weeks of treatment, the difference of IPSS score decline and 97.5% CI of the three groups were calculated. If the lower limit of unilateral 97.5% confidence interval of the difference of IPSS score decline between Silodosin + placebo group and Tamsulosin + placebo group is greater than the non-inferiority threshold of 1 (-1 point), then "Silodosin + placebo" is not inferior to "Tamsulosin + placebo" group. If the lower limit of unilateral 97.5% confidence interval of the difference between the IPSS scores of Silodosin + Ningmitai group and Silodosin + placebo group is greater than the superior effect threshold of 2 (0 points), then "Silodosin + Ningmitai" is superior to "Silodosin +

placebo". Subgroup analysis was considered according to whether the NIH-CPSI pain score was ≥ 4 before treatment and the severity of IPSS total score.

②Secondary endpoint index: The changes of IPSS scores, IPSS sub-scores and QoL scores were compared between groups at 1, 2, 4, 8 and 12 weeks after treatment. The changes of Q_{max} , PVR, serum PSA and prostate volume were compared between groups by single factor analysis of variance or Wilcoxon rank sum test. Bonferroni method was used to adjust the test $\alpha = 0.0167$. The clinical progression curve of BPH was drawn by Kaplan-Meier; COX regression model was used to compare the factors affecting the clinical progression of BPH. The proportion of patients with IPSS total score decreased in severity was compared between groups by χ^2 test or Fisher exact probability method.

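### The FAS is the main set for the non-inferiority test as well as the superiority test, and nothing requires the PPS to support a non-inferiority claim

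*SAP*

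**What the plan says.** SAP section 1 (analysis populations) calls the FAS the main efficacy set: "The total analysis set is the main validity evaluation population of this study". Entry to it is wide: "all the randomized subjects with more than one medication record and effectiveness evaluation were included in the full analysis set". On the other set the SAP says "PPS is the secondary analysis population of validity, but if its results are inconsistent with the full analysis set, it is necessary to analyze" the discrepancy in detail. It does not say what is then concluded.

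The PPS is defined by alternatives: "Include all subjects who have completed the treatment stipulated in the scheme or have not seriously violated the trial scheme". What counts as a serious violation is left open: "The exact definition of the serious violation scheme will be finalized during the data review". The SAP does not say that this review is blind.

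SAP section 2(1) plans a non-inferiority test of silodosin + placebo against tamsulosin + placebo and a superiority test of silodosin + Ningmitai against silodosin + placebo, each at one-sided 0.025. Section 2(3) says of the efficacy analysis: "Conducted in FAS and PPS at the same time". The non-inferiority rule in item 1 of that section asks whether the lower limit "is greater than the non-inferiority threshold of 1 (-1 point"), and it names no analysis set.

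**The concern.** One population rule serves two tests that react differently to non-adherence. Subjects who stop treatment or take it poorly usually make arms look more alike. In a superiority test that works against the claim, so the FAS is the cautious choice. In a non-inferiority test it can work for the claim. The PPS is the planned analysis that bears most directly on this, yet no rule makes the conclusion depend on it.

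The trial offers scope for such dilution. The protocol allows for 20% dropout. IPSS is recorded at weeks 1, 2, 4 and 8 as well as week 12, so a subject who stops early can still meet the FAS definition.

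At stake is the meaning of the silodosin claim. If the FAS limit clears -1 and the PPS limit does not, the plan permits a claim of non-inferiority, and the weight given to the PPS would be argued after the results are known.

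**Working it through.** **The plan's own figure.** The protocol summary plans 312 subjects, allowing for 20% dropout, allocated 1:1:1. That is 312/3 = 104 per arm. Dividing by the retention rate, 83/(1 - 0.20) = 103.75, rounded up to 104, so 83 evaluable per arm is consistent with the plan. It is an inference: 86 × 1.20 = 103.2 also rounds up to 104. The documents give no SD, power or assumed true difference, so the base number itself cannot be reproduced.

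**Inputs.** From the documents: margin -1, one-sided 0.025, 104 per arm, 20% dropout. Assumed:
- SD of IPSS change 4 to 6, with smaller values shown as well;
- all 104 per arm in the FAS and 83 per arm in the PPS;
- a true on-treatment difference (silodosin minus tamsulosin, in IPSS decline) of exactly -1;
- no arm difference in the 20% of FAS subjects outside the PPS.

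**Chance of a FAS claim.** The expected FAS difference is 0.8 × (-1) = -0.8, and SE = SD × √(2/104). The claim is made with probability P(Z > 1.960 - 0.2/SE). At SD 5, SE = 0.693 and 0.2/0.693 = 0.288, so P(Z > 1.672) = 4.7%.

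**Chance that both sets pass.** The PPS difference is centred on -1 with SE = SD × √(2/83), so the PPS alone passes 2.5% of the time. The PPS is contained in the FAS, so the two estimates correlate at √(83/104) = 0.893. The joint probability comes from the bivariate normal distribution.

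| SD | FAS SE | Z needed | FAS claim | Both pass | FAS passes, PPS fails |
|---|---|---|---|---|---|
| 4 | 0.555 | 1.599 | 5.5% | 2.1% | 3.4% |
| 5 | 0.693 | 1.672 | 4.7% | 1.9% | 2.8% |
| 6 | 0.832 | 1.720 | 4.3% | 1.9% | 2.4% |

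At smaller SDs the excess is larger: a FAS claim has probability 7.0% at SD 3 and 10.8% at SD 2, against 2.2% and 2.4% when both sets must pass.

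**Cost in power.** With a true difference of 0 in both sets, each set passes with probability P(Z < 1/SE - 1.960), using that set's SE.

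| SD | FAS alone (104) | PPS alone (83) | Both |
|---|---|---|---|
| 2.3 | 0.88 | 0.80 | 0.785 |
| 3 | 0.67 | 0.57 | 0.54 |
| 5 | 0.30 | 0.25 | 0.21 |

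For orientation, 83 per arm gives 80% power only at SD = √(83/2)/(1.960 + 0.842) = 2.3.

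**The case against.** A reader might infer that non-inferiority is decided in the FAS alone, that it would be declared whatever the PPS shows, and that dropout will pull the arms together. The documents support none of these as stated. Efficacy is run in both sets, the -1 rule names no set, and a disagreement must be examined. The supportable statement is that such a claim *could* be made, because the FAS is the main set and no rule prevents it.

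Dilution is likewise assumed, not shown. Subjects with no efficacy evaluation are outside the FAS, and the SAP gives no missing-data method, so a dropout without a week-12 IPSS may contribute nothing to the comparison. The 20% in the protocol is a dropout allowance; it is not a count of subjects who stay in the FAS with no arm difference. Unequal dropout could also move the estimate against silodosin. All this stands, and it makes the figures an illustration only.

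The excess over 2.5% is an error rate only if the on-treatment difference is the target. If the target is the difference among all FAS subjects, its true value in the illustration is -0.8, and a claim there is not false. That also stands.

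Finally, a PPS failure does not prove dilution. The PPS is smaller and is selected after randomization. With a true difference of 0, the FAS passes and the PPS fails in about 6% to 13% of trials for SD 2 to 6. At SD 5 this is 9.1%, compared with 2.8% when the true difference is -1. Discordance is therefore realistic and ambiguous. That weakens the PPS as a detector of dilution, but it is also a reason to fix its consequence in advance.

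**Conclusion.** The point holds as a gap in the decision rule. The plan permits a non-inferiority claim on the FAS with a PPS limit at or below -1, and it does not say what is concluded if the two sets disagree. The illustrated excess is moderate: about 4.3% to 5.5% at SD 4 to 6 against 2.5%, and higher at smaller SDs. It depends on the assumed SD, on 20% of the FAS showing no arm difference, and on the on-treatment difference being the target. The documents establish neither the size nor the direction of any bias in this trial. The superiority comparison is not affected, because the FAS is a suitable deciding set for it. This is a cheap improvement that should be made.

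**What to change.** Three changes of SAP wording, to be made together:

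1. In section 2(3), item 1, add: *Non-inferiority of silodosin + placebo to tamsulosin + placebo is concluded only if the lower limit exceeds -1 in both the FAS and the PPS. Superiority of silodosin + Ningmitai over silodosin + placebo is decided in the FAS.*
2. In section 1(2), replace 'or' with 'and', so that the PPS holds subjects who completed treatment and had no serious violation. As written, it can admit non-completers or violators and so keep the dilution that the PPS is meant to remove.
3. Fix the list of serious violations before unblinding, since it now bears on the decision.

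Both analyses are already planned, so no new data or visits are needed. The cost is power when the drugs are truly equal. Relative to the FAS alone the loss is material: 0.67 to 0.54 at SD 3 and 0.30 to 0.21 at SD 5. Relative to the 83 evaluable per arm implied by 312 and 20% dropout, it is small at SD 2.3 and 3: 0.80 to 0.785 and 0.57 to 0.54. If the tightened PPS falls below 83 per arm, the loss will be larger.

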The Efficacy and Safety of Silodosin Singly or Combined with Ningmitai Capsules in the Treatment of Benign Prostatic Hyperplasia (BPH) Complicated with Lower Urinary Tract Symptoms (LUTS) —A Multicenter, Prospective, Randomized, Doubleblind, Positive Controlled Study

Date: September 8, 2022

Research Proposal Summary

Scheme number	NM-22-A-001-YJ-001					
Scheme name	The Efficacy and Safety of Silodosin Capsules Singly or Combined with Ningmitai Capsules in the Treatment of Benign Prostatic Hyperplasia					
Version number/date	Version 1.0, December2, 2021					
sponsor	Shanghai Haitian Pharmaceutical Technology Development Co., Ltd.					
Clinical trial staging	Post-marketing clinical re-evaluation					
test drug	Ningmitai Capsules (Ningmitai [®] , Z20025442), each 0.38g, was produced by Guiyang Xintian Pharmaceutical Co., Ltd.					
	Silodosin Capsules (Qianweitai®, H20213612), each 4mg, was produced by Shanghai Huilun Pharmaceutical Co., Ltd.					
	Tamsulosin Hydrochloride Sustained Release Capsules(H20000681), each0.2mg, was produced by Astellas Pharma Inc.					
	Placebo, Ningmitai capsule simulator, each0.38g, was produced by Guiyang Xintian Pharmaceutical Co., Ltd.					
Indications	Benign Prostatic Hyperplasia with Lower Urinary Tract Symptom					
Test purposes	1.To evaluate the efficacy and safety of Silodosin Capsules alone versus Tamsulosin Hydrochloride Sustained Release Capsules in the treatment of BPH with lower urinary tract symptoms.					
	2.To evaluate the efficacy and safety of Ningmitai Capsules combination with Silodosin Capsules versus Silodosin Capsules alone in the treatment of BPH with lower urinary tract symptoms.					
Research design	A multicenter, prospective, randomized, controlled clinical trial design					
total number	It is planned to complete 312 cases (considering the 20% dropout rate)					
number of research	8					

centers					
Study period	6 months				
research	Diagnostic criteria:				
object	1. Male Subjects aged 60 ~ 80 years, clinically diagnosed as benign prostatic hyperplasia.				
	2. Has an IPSS score ≥ 8 points at Screening and Baseline.				
	3. Has a $4 \le Q_{max} \le 15$ ml/s when urination volume > 150 ml.				
	4. Has a prostate volume (PV) \geq 30 ml by ultrasound examination.				
	5. Subjects who can read, understand, and complete the research questionnaire.				
	6. Subjects willing to participate voluntarily in this clinical trial, give informed consent and sign				
	informed consent.				

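### The silodosin-versus-tamsulosin primary rule stops at non-inferiority and forgoes an inexpensive pre-specified superiority step on the same interval

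*SAP*

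**What the plan says.** - **Hypothesis.** SAP 2(1) General principle states that "the changes of IPSS scores between Tamsulosin + placebo group and Silodosin + placebo group were compared by non-inferior test". The combination is compared with silodosin by a superiority test. Each test is at one-sided 0.025.
- **Decision rule.** SAP 2(3), Main endpoint indicators, begins "If the lower limit of unilateral 97.5% confidence interval of the difference of IPSS score decline between Silodosin + placebo group and Tamsulosin + placebo group" and requires that limit to be "greater than the non-inferiority threshold of 1 (-1 point"). The only conclusion it then draws is that silodosin is not inferior. The zero threshold, "greater than the superior effect threshold of 2 (0 points"), is given only for the combination against silodosin. I read the 1 and 2 as labels and the bracketed values as the thresholds.
- **Secondary tests.** SAP 2(3), Secondary endpoint index, says "The changes of IPSS scores, IPSS sub-scores and QoL scores were compared between groups at 1, 2, 4, 8 and 12 weeks after treatment". SAP 2(1) puts secondary indices at 0.0167 after Bonferroni adjustment and other hypotheses at two-sided 0.05.
- **Endpoint list.** In both documents, change in IPSS total at week 12 is the primary endpoint, and IPSS total is secondary only at weeks 1, 2, 4 and 8.
- **Purpose.** The first aim in the Protocol summary (Test purposes) is "To evaluate the efficacy and safety of Silodosin Capsules alone versus Tamsulosin Hydrochloride Sustained Release Capsules", for BPH with lower urinary tract symptoms.

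**The concern.** A lower limit above 0 is necessarily also above -1. Once non-inferiority is shown, the same limit can therefore be compared with 0 as a nested second step, without raising the error for this comparison above 0.025. The plan does not provide for this. If silodosin turned out clearly better than tamsulosin, the pre-specified primary conclusion would still be only that it is not inferior, and a superiority statement would be post hoc or would rest on a secondary test whose existence and level are unclear.

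The question is likely to arise. With a margin of 1 point and the assumed SDs below, non-inferiority is reached only if silodosin is observed to be better than tamsulosin.

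**Working it through.** **Inputs from the documents.** Margin -1 point; primary level one-sided 0.025; secondary level 0.0167; 312 patients allocated 1:1:1, with 20% dropout considered.

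**Assumed inputs.** The documents give no SD, expected difference or power. I use SD 4, 5 and 6 and true advantages of 2 points and 1 point. Evaluable patients per arm are also assumed: 83, with 104 as the upper case.

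**The plan's own figures.**
- 0.05/3 pairwise comparisons = 0.01667, which reproduces 0.0167.
- 83/(1 - 0.20) = 103.75, rounded up to 104; 104 × 3 = 312. The total therefore fits 83 evaluable per arm. The FAS need not lose the full 20%, so 104 is shown as well.

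**Observed difference needed for non-inferiority.** SE = SD × √(2/n). At SD 5 and n = 83, SE = 5 × √(2/83) = 0.776. The smallest qualifying difference is -1 + 1.960 × 0.776 = +0.52 points (SD 4: +0.22; SD 6: +0.83). It is above zero for any SD over about 3.3, since 1/(1.960 × √(2/83)) = 3.29. At 104 per arm and SD 5, SE = 0.693 and the value is +0.36.

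**Power for superiority.** Power = Φ(δ/SE - z), with z = 1.960 for the follow-on step and 2.393 for two-sided 0.0167. The ratio is 2.393/1.960 = 1.22, so the 0.0167 test needs an observed difference 22% larger. At SD 5, n = 83 and δ = 2: 2/0.776 = 2.577; Φ(0.617) = 0.731 and Φ(0.184) = 0.573.

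| n per arm | SD | True advantage | Follow-on step | At 0.0167 |
|---|---|---|---|---|
| 83 | 4 | 2 | 90% | 80% |
| 83 | 5 | 2 | 73% | 57% |
| 83 | 6 | 2 | 57% | 40% |
| 83 | 5 | 1 | 25% | 13% |
| 104 | 5 | 2 | 82% | 69% |

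**Error rates.** Three arms were simulated (4 million draws, 83 per arm, SD 5), comparing the lower limit with -1 and then with 0.
- For silodosin against tamsulosin with the added step, the chance of a false claim is 0.0249 at a true difference of -1, 0.0046 at -0.5 and 0.0249 at 0. Superiority never occurred without non-inferiority.
- Over both primary comparisons, the worst case is a silodosin-tamsulosin difference of -1 with a combination-silodosin difference of 0. The error there is 0.050 with or without the step.
- If both true differences are 0, the chance of any false primary claim is 0.025 as planned and 0.050 with the step. As planned, declaring non-inferiority is correct in that case, so only the combination claim can be false.

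**The case against.** **Stopping at non-inferiority against an active control is a legitimate choice.** This stands. A reader might infer from the first purpose that superiority was required. The documents do not support that: both purposes use the same general wording, and one is tested for non-inferiority and the other for superiority.

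**A reader might infer that the only other route is a test at 0.0167, so the plan wastes power.** The documents do not establish this. The secondary paragraph's list of weeks is loose: it also gives QoL weeks 1 and 2, while the endpoint list has QoL only at weeks 4, 8 and 12. If the endpoint list governs, there may be no secondary difference test of week-12 IPSS total for this pair, or such a test may fall under the two-sided 0.05 default, which sets the same bar as the follow-on step. The power comparison with 0.0167 applies only if the secondary paragraph governs.

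**A reader might infer that the step costs no alpha at all.** That holds within this comparison and for the worst case, but not when both true differences are 0.

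**The interval will be calculated anyway.** This also stands: a limit above 0 can be read from it with the same error for this comparison. What is lost is the pre-specified status of the claim, not the evidence.

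**The gain depends on an assumed effect.** It does. Two points is twice the margin; at 1 point the added step would fail about three times in four.

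**Conclusion.** The point holds as an optional, low-cost improvement. The primary rule for silodosin against tamsulosin has no step against 0, and adding one is statistically sound. It is not an error in the plan: the non-inferiority rule is complete and its conclusion valid without the step.

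If the alternative is a test at 0.0167, the gain at 83 per arm is 10 to 17 percentage points of power for a true 2-point advantage over SD 4 to 6, and about 12 points for a 1-point advantage at SD 5. If the alternative is no test, or one at two-sided 0.05, the gain is a pre-specified claim and a clear place for it in the plan. SD, true difference and evaluable number are all assumptions. The error results do not depend on the true difference being favourable to silodosin.

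**What to change.** Before unblinding, add to SAP 2(3), Main endpoint indicators:

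*If non-inferiority of Silodosin + placebo is shown, superiority over Tamsulosin + placebo is then tested in the FAS on the same one-sided 97.5% lower limit (> 0).*

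State also that week-12 IPSS total for this pair is not tested again among the secondary comparisons at 0.0167. This settles the conflict between the secondary paragraph and the endpoint list for this variable.

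If the sponsor wants 0.025 across both primary comparisons, the order of all three tests (non-inferiority, superiority over tamsulosin, superiority of the combination) must be stated. Otherwise, acknowledge that each primary comparison carries its own 0.025.

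The cost is a sentence or two in the SAP, with no extra patients or data, plus the rise from 0.025 to 0.050 in the chance of any false primary claim when both true differences are 0.

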Course of treatment: 12 weeks

Visit points: screening period, days -28 to 0), after 1 week of treatment (day 7 ± 2), after 2 weeks of treatment (day 14 ± 3), after 4 weeks of treatment (day 28 ± 5), after 8 weeks of treatment (day 56 ± 7), after 12 weeks of treatment (day 84 ± 10).

Research steps

This trial is divided into two stages: screening period, treatment period and follow-up period.

Screening period (days -28 to 0): After signing the informed consent form, the subjects entered the screening period, and made a 24-hour urination diary and screening examination.

Treatment and Follow-up period: eligible patients were randomly assigned to three groups according to 1: 1: 1 and received Tamsulosin + placebo, Silodosin + placebo or Silodosin + Ningmitai for 12 weeks. During the treatment period, the subjects' diaries were recorded according to the requirements of the scheme, and they were followed up at 1 week (7 ± 2 days), 2 weeks (14 ± 3), 4 weeks (28 ± 5 days), 8 weeks (56 ± 7 days) and 12 weeks (84 ± 10 days). During the visit, relevant scale scores and laboratory examinations were performed, and the occurrence of adverse events during the follow-up was recorded to evaluate the safety.

study endpoint

Primary endpoint:

International Prostate Symptom Score (IPSS), Changes of scores at the 12th week of treatment compared to the baseline scores.

Secondary endpoints:

1.IPSS Score

- ①changes of IPSS total score: Changes of IPSS scores at 1, 2, 4 and 8 weeks after treatment compared with baseline scores
- ②Proportion of patients with IPSS total score severity decreased by at least one grade at 12 weeks
- ③IPSS sub-score: IPSS Stimulation Score at 1, 2, 4, 8, 12 weeks (Sum of Question 2, 4, 7) and

Changes of IPSS obstruction score (sum of question 1, 3, 5, 6) compared with baseline.

- 2.Quality of life (QoL) score: Changes in scores at 4, 8 and 12 weeks of treatment compared with baseline
- 3. Maximum urinary flow rate (Q_{max})

The change of Q_{max} at 12 weeks of treatment compared with baseline.

4. Patient response rate

Patient response rate is defined as the proportion of patients whose IPSS total score decreased by \geq 25% and Q_{max} .

increased by $\geq 30\%$ compared with baseline value after treatment.

5. Residual urine volume (PVR)

Changes of PVR at 12 weeks of treatment compared with baseline.

6. Prostate specific antigen (PSA)

Changes of PSA at 12 weeks of treatment compared with baseline.

7. Prostate volume (PV)

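### Secondary endpoints are tested by single-step Bonferroni at 0.0167; Holm's step-down on the same three p-values keeps the per-endpoint 5% bound and never rejects fewer hypotheses

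*SAP*

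**What the plan says.** SAP section 2(1) (General principle) tests the non-primary hypotheses two-sided at 0.05 and then says "the secondary index was adjusted by Bonferroni method with a test level of" 0.0167. SAP section 2(3), item ② (Secondary endpoint index) repeats it for the between-group comparisons: "Bonferroni method was used to adjust the test" level, again 0.0167. No step-down or other sequential procedure is mentioned. Neither section states the divisor or lists the pairs of arms to be compared.

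The design has three arms: "eligible patients were randomly assigned to three groups according to 1: 1: 1" (protocol, Research steps). In the protocol's labels, A is tamsulosin + placebo, B is silodosin + placebo and C is silodosin + Ningmitai. The protocol's two purposes are B versus A ("To evaluate the efficacy and safety of Silodosin Capsules alone versus Tamsulosin Hydrochloride Sustained Release Capsules") and C versus B ("To evaluate the efficacy and safety of Ningmitai Capsules combination with Silodosin Capsules versus Silodosin Capsules alone"). The SAP's primary tests cover those same two contrasts, each at one-sided 0.025.

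**The concern.** Single-step Bonferroni compares all three p-values with 0.05/3, even after one or two hypotheses have been rejected and fewer remain in question. Holm's procedure uses the same three p-values and relaxes the threshold as hypotheses fall. It therefore rejects everything that Bonferroni rejects, and sometimes more, under the same family-wise guarantee within an endpoint.

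What is at stake is power for the secondary comparisons covered by the 0.0167 rule, such as Qmax, QoL, the IPSS sub-scores and PVR. The responder proportion is less clear: item ② gives no test for it, so only the general sentence in section 2(1) could bring it under the rule. Neither the validity of the secondary tests nor the primary analysis is in question.

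**Working it through.** **1. The plan's own figure.** Three arms give 3 pairs. 0.05/3 = 0.016667, which rounds to 0.0167. The protocol numbers eight secondary endpoints, so 3 is not the number of endpoints. Three pairwise comparisons per endpoint is the natural reading, but it remains an inference.

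**2. Assumption.** The documents give no effect size or SD for any secondary endpoint. As a benchmark, take a contrast with 80% power at unadjusted two-sided 0.05. Its noncentrality is 1.960 + 0.842 = 2.802.

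**3. Power under the present rule.** The two-sided critical value at 0.0167 is 2.394. Power = P(Z > 2.394 − 2.802) = P(Z > −0.408) = 65.8%.

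**4. Power under Holm on three pairs.** The smallest p-value is tested against 0.0167, the next against 0.025 and the largest against 0.05, stopping at the first failure. This was simulated with three normal arm means and equal arms, so that B vs A and C vs B share arm B and have correlation −0.5. Each real stated contrast has noncentrality 2.802.

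| True state | Bonferroni | Holm, three pairs | Gain (points) |
|---|---|---|---|
| One stated contrast real, the other null | 65.8% | 69.1% | 3.3 |
| Both real, opposite directions (C equal to A) | 65.8% | 69.1% | 3.3 |
| Both real, same direction | 65.8% | 78.7% | 12.9 |

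The figures are power for a real stated contrast. In the last row C vs A has twice the effect and is almost always rejected first, which leaves 0.025 and 0.05 for the two stated contrasts. In the second row C vs A is null and gives no such help.

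**5. On the trial's scale (assumed standardised difference 0.4).** 312/3 = 104 per arm; 104 × 0.8 = 83.2, so about 83 evaluable after 20% dropout. Noncentrality is 0.4 × √(83/2) = 2.577, and power at 0.0167 is P(Z > 2.394 − 2.577) = 57.3%. Holm on three pairs gives about 60% if one stated contrast is real and about 70% if both are real in the same direction.

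**6. Error rates, per endpoint.** With all three arms equal, the simulated family-wise error is 4.4% under Bonferroni and 4.4% under Holm. With C vs B real at the benchmark size and B vs A null, the false-positive rate for B vs A is 1.7% under Bonferroni and 3.2% under Holm. Both are within 5%, but they are not equal.

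**7. Restricting the family to B vs A and C vs B.** Each contrast would get 0.05/2 = 0.025, with critical value 2.241. Power = P(Z > 2.241 − 2.802) = 71.2%. Holm over these two gives 71.4% if one is real, about 76.5% if both are real in opposite directions and 78.7% if both are real in the same direction. The false-positive rate of a null B vs A when C vs B is real becomes 4.1%.

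**The case against.** **The plan contains no error here.** Bonferroni at 0.0167 is pre-specified, valid and stated consistently in both places. This stands: the point concerns efficiency on secondary endpoints only.

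**Holm's extra power is not free.** The realised false-positive rate of a null contrast rises once another contrast is rejected (1.7% to 3.2% in step 6). The SAP makes no adjustment across eight numbered secondary endpoints, some measured at up to five visits, so this would loosen the only correction present. Single-step Bonferroni also has simple simultaneous intervals that match its tests (1 − 0.0167 = 98.3% each), and Holm has none as simple. Both costs are real. Neither breaks the per-endpoint 5% bound, which is the only family-wise protection that the present rule gives.

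**C vs A may be wanted.** A reader might infer that a share of alpha is wasted on tamsulosin versus the combination, because neither purpose names that pair, and that it should be made descriptive. The documents do not support going that far. The SAP never names the pair. The title describes a positive-controlled study of silodosin alone or combined with Ningmitai, and tamsulosin is the only arm without silodosin. The SAP also calculates the primary differences across the three groups. Comparing the combination with the active control is a legitimate secondary question, and dropping it is a trade-off for the sponsor to weigh.

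**Conclusion.** The point holds as a modest, inexpensive improvement. For the three pairwise comparisons within each secondary endpoint, Holm never rejects fewer hypotheses than Bonferroni, has the same 5% family-wise bound and gives up no comparison. Under the 80% benchmark the gain is about 3 points when one stated contrast is real or the two effects oppose each other, and about 13 points only when both are real in the same direction.

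Two stronger readings should be resisted. A reader might take the 13-point gain as what Holm delivers whenever both effects are real; with opposite directions it is about 3. Nor do the documents make the favourable case the expected one: the SAP tests silodosin against tamsulosin for non-inferiority on the primary endpoint, so the plan does not rest on silodosin being better. A reader might also take identical error control from the shared bound; the bound is the same, but the realised error for a null contrast is higher.

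The size of the gain rests on an assumed effect, since the documents give none for the secondary endpoints, and the family of three rests on the inferred divisor. That Holm never rejects fewer hypotheses on the same p-values does not depend on the assumed effect size.

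**What to change.** In SAP sections 2(1) and 2(3), item ②, replace the Bonferroni rule at 0.0167 with wording such as:

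> For each secondary endpoint, the three pairwise comparisons (B vs A, C vs B, C vs A) are tested two-sided with Holm's procedure: the ordered p-values are compared with 0.0167, 0.025 and 0.05, stopping at the first that is not significant. Family-wise error is controlled at 5% within each endpoint; no adjustment is made across endpoints or visits.

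This also makes the SAP name its comparisons and state what its error control covers. It should be settled before unblinding. The cost is SAP wording, plus the loss of simple simultaneous intervals that match the tests; the SAP should say which intervals will be reported and that they do not correspond exactly to the Holm decisions.

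Optionally, the sponsor may limit the family to B vs A and C vs B, with Holm thresholds 0.025 and 0.05. That raises power further when only one stated contrast is real (71.4% against 69.1%), but gives up formal testing of C vs A.
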